5.4.4 Procedural Exclusions

- 43. Unable to swallow capsules once daily.
- Known sensitivity to 18F-MK-6240.
- Poor venous access.
- 46. Has any of the following contraindications to having a LP, including, but not limited to:
 - Screening values of platelet count and coagulation parameters including INR, prothrombin time, and partial thromboplastin time or other coagulopathy should be within normal ranges. Participants with nonclinically significant and stable out-of-range values may be eligible to enroll in the study at the discretion of the Investigator.
 - Administration of any antiplatelet or anticoagulant medication (e.g., aspirin [unless ≤ 325 mg/day], clopidogrel, dipyridamole, warfarin, dabigatran, rivaroxaban, and apixaban) that cannot be safely held before and/or after an LP procedure according to local or institutional guidelines and/or Investigator determination.
 - Presence of risk for increased or uncontrolled bleeding and/or risk of bleeding that is not managed optimally and could place a participant at an increased risk for procedural bleeding. These could include, but are not limited to, known anatomical factors at or near the LP site (e.g., vascular abnormalities, neoplasms, or other abnormalities).
 - Lumbar spine deformity and/or known evidence on MRI contraindicating LP.
 - Clinical signs or symptoms detected during neurological exam (e.g., focal neurological signs, altered mental status, papilledema) or radiographic evidence (e.g., enlarged ventricles, herniation, or mass effect) of increased intracranial pressure.

ASN51-201 Asceneuron SA

Any symptoms caused by or related to the LP if performed during Screening must be resolved prior to randomization.

- Contraindication to MRI.
- 48. Contraindication to having a PET scan (e.g., inability to lie flat or still for the duration of the scan) or intolerance to previous PET scans (i.e., previous hypersensitivity reactions to any PET radioligand, imaging agent, or any of the excipients; failure to participate in and comply with previous PET scans).
- 49. Planned or recent exposure to ionizing radiation that when combined with study PET imaging procedures would result in a cumulative exposure to radiation that exceeds local limits.

5.4.5 Other Exclusions

- 50. Participant living in an organized care facility with extensive intervention and/or support of daily living activities (e.g., a nursing home).
- 51. Blood donation (1 unit or more) within 90 days prior to Screening Visit 1, plasma donation from 1 week prior to Screening Visit 1, and platelet donation from 6 weeks prior to Screening Visit 1.
- Inability to comply with study requirements.
- 53. Other unspecified reasons that, in the opinion of the Investigator or the Sponsor, make the participant unsuitable for enrollment.

5.5 Lifestyle Considerations

5.5.1 Meals and Dietary Restrictions

No restrictions.

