	Woman of childbearing potential (per CTFG 2020)
	 Positive urine drug test at Screening. Testing positive for benzodiazepines or opioids in urine drug testing is permitted if determined by the Investigator to be due to appropriate medical use and not drug abuse.
	Any prior or ongoing exposure to active or passive anti-amyloid immunotherapy, anti-tau immunotherapy, an anti-tau antisense oligonucleotide or gene therapy, or O-GlcNAcase inhibitor
	Requires use of anticoagulants during trial participation
	Any evidence of hepatic impairment (Child Pugh classification B and C are excluded)
	Requires use of moderate or strong CYP3A4 inhibitors during trial participation
	Requires use of moderate or strong CYP2C19 inhibitors during trial participation
	Additional eligibility criteria are described in the protocol.
Duration of	Up to approximately 76 weeks, including:
Participation	A pre-screening period of up to 12 weeks (within 12 weeks of randomization)
	A screening period of up to 8 weeks (within 8 weeks of randomization)
	A placebo-controlled DB Intervention Period of 24-weeks
	An LTE period of 36 weeks
	A follow-up period of 4 weeks.
Trial Periods	Prescreening period of up to 12 weeks, which includes the collection of medical history and plasma sample for pTau 217 and APOE genotype, may occur prior to the Screening period
	Screening period of up to 8 weeks
	 Double-blind Placebo-Controlled Intervention Period (24 weeks, Week 1 to end of Week 23)
	 Visits every 2 to 4 weeks; each visit may take place over more than 1 day if necessary
	Long-term Extension Period (36 weeks; Weeks 24 to Week 60)
	 Visits every 2 to 4 weeks from weeks 24 to 48 and then every 6 weeks; each visit may take place over more than 1 day if necessary.
	Participants who withdraw from the study prematurely are to return to the study site for an Early Termination (ET) Visit and assessments and for the Follow-up Safety Visit 4 weeks after the last administration of study intervention.
Statistical Methods	Trial data will be reported using summary tables, figures, and data listings. Descriptive statistics will be used to summarize the data. For continuous variables, the mean, standard deviation, median, minimum, and maximum will be provided. For discrete data, incidence and percentages will be provided. Statistical tests will be 1-sided at the alpha level of 0.10, unless stated otherwise. P-values will be used descriptively and will have no inferential value.

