5.4.3 Exclusion Criteria by Concomitant Medications/Prior Therapies

- 33. Initiation or change in dose of an acetylcholinesterase inhibitor and/or memantine within less than 8 weeks prior to randomization.
- 34. Positive urine drug test at Screening. Testing positive for benzodiazepines or opioids in urine drug testing is permitted if determined by the Investigator to be due to appropriate medical use and not drug abuse. Medical cannabidiol (CBD) use is permitted if prescribed by a medical provider in accordance with local laws and if in the opinion of the Investigator its use does not pose a risk to participant safety or compromise a participant's performance on cognitive assessments.
- 35. Taking medications known to prolong PR or QT intervals (e.g., calcium channel blockers or beta blockers) unless on a stable dose of (or titrating) within 12 weeks prior to randomization.
- 36. Use of any medications that, in the opinion of the Investigator, may contribute to cognitive impairment, put the participant at higher risk for AEs, or impair the participant's ability to perform cognitive testing or complete study procedures.

- 37. Any prior or ongoing exposure to active or passive anti-amyloid immunotherapy, anti-tau immunotherapy, an anti-tau antisense oligonucleotide or gene therapy, or O-GlcNAcase inhibitor.
- 38. If previously exposed to an investigational product other than active or passive anti-amyloid immunotherapy, anti-tau immunotherapy, an anti-tau antisense oligonucleotide or gene therapy, or O-GlcNAcase inhibitor, then 12 weeks or 5 half-lives (whichever is longer) must have passed prior to randomization.
- Known allergy to any components of the ASN51 formulation.
- 40. Requires use of anticoagulants during trial participation (to permit safe CSF collection).
- 41. Prior use of a moderate or strong inhibitor of CYP3A4 within a period of 5 half-lives of randomization (refer to Appendix 16).
- 42. Prior use of a moderate or strong inhibitor of CYP2C19 within a period of 5 half-lives of randomization (refer to Appendix 16).

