6.8.1 Prohibited Concomitant Therapy

To be eligible for the trial, participants must not require chronic daily drug intake of the medications listed below. If participants discontinue any of these medications prior to randomization, a washout period of the lesser of 5 half-lives or 30 days is required.

The following medications will remain prohibited throughout the DB Intervention Period:

- Any investigational product intended for AD (e.g., anti-tau antisense oligonucleotide or gene therapy, active or passive anti-amyloid immunotherapy, active or passive anti-tau immunotherapy, O-GlcNAcase inhibitor, etc.) or other investigational product within 8 weeks prior to randomization
- Anticoagulants
- Moderate and strong inhibitors of CYP3A4 and CYP2C19 (refer to Appendix 16).

During the LTE Period, use of prohibited/restricted medications will be addressed on a case-bycase basis in consultation with the Sponsor Medical Monitor.

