5.4.2 Exclusion Criteria by Screening Assessments, Section 6.8.1, and Appendix 16	41. Prior use of a strong inhibitor of CYP3A4 within a period of 5 half-lives of randomization (refer to Appendix 16). 42. Prior use of a strong inhibitor of CYP2C19 within a period of 5 half-lives of randomization (refer to Appendix 16).	41. Prior use of a moderate or strong inhibitor of CYP3A4 within a period of 5 half-lives of randomization (refer to Appendix 16). 42. Prior use of a moderate or strong inhibitor of CYP2C19 within a period of 5 half-lives	Major. Updated list of exclusionary medications based on FDA feedback.

Protocol Section	Original Text	Revised Text	Justification
		of randomization (refer to Appendix 16).	

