		Appendix 16 updated to include:	
		Moderate 3A4 inhibitors: Aprepitant, ciprofloxacin, conivaptan, crizotinib, diltiazem, dronedarone, fluconazole, grapefruit juice, imatinib, isavuconazole,	
		and verapamil Moderate 2C19 inhibitors: Cenobamate, felbamate, voriconazole	
8.7	Participants should be contacted by	Participants should be	Minor. Clarified
Pharmacokinetics	telephone about 1 business day before indicated visits to remind them to bring IMP to the investigative site for administration during the visit.	contacted by telephone about 1 business day before indicated visits to remind them to bring IMP to the investigative site for administration during the visit, and to record the time IMP is taken on the day prior to the visit.	PK procedures.
10.3 Informed Consent Process	The Investigator is responsible for obtaining written informed consent from each potential trial participant prior to the conduct of any trial procedures.	The Investigator is responsible for obtaining written informed consent from each potential trial participant and study partner prior to the conduct of any trial procedures.	Minor. No change to consent process, only updating text for clarity.
13.2 Clinical Laboratory Tests Table 8 Clinical Laboratory Tests	Follicle stimulating hormone (Screening; local laboratory)	Follicle stimulating hormone (Screening; local or central laboratory)	Minor. Clarification of laboratory procedure.

Protocol Section	Original Text	Revised Text	Justification
13.2 Clinical Laboratory Tests Table 8 Clinical Laboratory Tests	Collection of CSF in polypropylene tubes. Cell count, protein, glucose.	Collection of CSF in polypropylene tubes. Cell count (white blood cells with differential and red blood cells), protein, glucose.	Minor. Clarification of laboratory testing.
Investigator Signature Page	A Phase 2, Double Blind, Randomized, Placebo Controlled Dose ranging Safety Trial of ASN51 in Adults with Early Alzheimer's Disease	A Phase 2, Randomized, Double-Blind, Placebo- Controlled, Parallel Group Study of ASN51 in Adults with Early Alzheimer's Disease	Minor. Corrected protocol title on investigator signature page.

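### Section 5.5.1 sets no dietary limits and points to no exception, while exclusion 41 and Section 6.8.1 bar moderate CYP3A4 inhibitors through Appendix 16, which is reported to list grapefruit juice

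*Combined protocol and SAP*

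**What the plan says.** Protocol Section 5.5.1, whose heading covers both meals and dietary restrictions, consists of "No restrictions". It refers to no other section.

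Three current passages restrict CYP3A4 inhibitors:

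- Synopsis (1.1), key exclusions: "Requires use of moderate or strong CYP3A4 inhibitors during trial participation".
- Section 5.4.3, exclusion 41: "Prior use of a moderate or strong inhibitor of CYP3A4 within a period of 5 half-lives of randomization (refer to Appendix 16"). Exclusion 42 says the same for CYP2C19.
- Section 6.8.1: under the lead-in "The following medications will remain prohibited throughout the DB Intervention Period", it lists "Moderate and strong inhibitors of CYP3A4 and CYP2C19 (refer to Appendix 16"). In the long-term extension, such use is settled case by case with the Medical Monitor.

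The body of Appendix 16 is not in the text available. The Revised Text column of the summary of changes reports what was added to it: "Moderate 3A4 inhibitors: Aprepitant, ciprofloxacin, conivaptan, crizotinib, diltiazem, dronedarone, fluconazole, grapefruit juice, imatinib, isavuconazole", followed by verapamil, and "Moderate 2C19 inhibitors: Cenobamate, felbamate, voriconazole". The stated justification is "Major. Updated list of exclusionary medications based on FDA feedback".

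**The concern.** A coordinator or participant with a question about diet would look in Section 5.5.1. It gives an unqualified answer and no pointer to the inhibitor list. Followed literally, it permits grapefruit juice during the double-blind period, although the sponsor has put juice on the list that defines the barred inhibitors.

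What is at stake is a consistent instruction to sites and participants. The sponsor treats PR prolongation and AV block as adverse events of special interest (8.4.3.1), so sites should not have to guess about an item on its inhibitor list. The mismatch also leaves open whether reported juice intake is a protocol deviation. That bears on the Per Protocol and PK analysis sets, because 9.1.3 refers to disallowed concomitant medications and 9.1.4 to major deviations that confound PK.

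**Working it through.** The plan gives no figure to reproduce on this point. The check is a comparison of texts and a count.

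**1. Is the grapefruit entry current?** It stands in the Revised Text column, so it is not superseded wording. The same row changes the criteria from strong to moderate or strong inhibitors. That wording is now in force in the synopsis, exclusion 41 and 6.8.1, so the revision was carried out. The summary of changes is used here only as evidence of what Appendix 16 now contains.

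**2. Set the instructions side by side for grapefruit juice.**

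| Place | Period | Instruction |
|---|---|---|
| 5.5.1 | not limited | no restriction on meals or diet |
| Exclusion 41 | 5 half-lives before randomization | moderate or strong CYP3A4 inhibitors barred, per Appendix 16 |
| 6.8.1 | double-blind period | moderate and strong CYP3A4 inhibitors barred, per Appendix 16 |
| 6.8.1 | long-term extension | case by case |
| Appendix 16, as reported | not stated in the summary | juice listed as a moderate CYP3A4 inhibitor |

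If the bar covers everything Appendix 16 lists, 5.5.1 gives the opposite instruction for juice. If the bar covers drugs only, the juice entry has no practical effect. In both cases a reader cannot tell which was intended, and 5.5.1 does not help.

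**3. How many items are affected?** Reported additions:

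- Moderate CYP3A4: aprepitant, ciprofloxacin, conivaptan, crizotinib, diltiazem, dronedarone, fluconazole, grapefruit juice, imatinib, isavuconazole, verapamil = 11.
- Moderate CYP2C19: cenobamate, felbamate, voriconazole = 3.
- Total: 11 + 3 = 14, of which 1 is dietary and 14 − 1 = 13 are drugs.

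Section 5.5.1 is at odds with the reported list for that one item.

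**4. How many participants could it touch?** The plan has two ASN51 arms of 26, so 2 × 26 = 52 is the ceiling in the double-blind period. It is not an estimate of those affected, because the documents give no prevalence of intake.

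**5. Can an exposure effect be sized?** No. The text available gives no interaction ratio for ASN51 and no CYP3A4 share of its clearance, so none is assumed.

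**The case against.** The strongest reply is that the prohibition is about drugs. Section 6.8.1 concerns concomitant therapy, speaks of medications and frames its entry rule as chronic daily drug intake. Exclusion 41 sits among medication exclusions, the synopsis speaks of requiring use, and Appendix 16 is titled as medication guidance. No operative section in the text available names juice. Juice enters only through an appendix whose body we cannot see and which may already say how to handle it. The dosing instructions mentioned in 6.3 are also unavailable and may cover it.

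Section 5.5.1 can also be read as a fed/fasted rule. That fits dosing with or without food (6.3) and the absence of a fasting requirement for laboratory tests (8.3.4). The protocol places other intake limits, on alcohol and high-dose biotin, among the exclusion criteria. So 5.5.1 is not its complete list of intake limits, and a specific list would ordinarily govern over a general statement.

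Much of this stands. A reader might infer a flat contradiction between operative sections. The documents do not support that, because the reach of the bar to juice is inferred. What does not stand is the conclusion that 5.5.1 needs no change. Its heading covers diet as well as meals, 6.3 already states the food rule, and the sponsor did put a juice on the list. A general statement with no pointer invites the wrong answer.

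**Conclusion.** The point holds as a minor inconsistency. Section 5.5.1 states an unqualified dietary rule that does not fit the reported content of Appendix 16, to which exclusion 41 and 6.8.1 refer. It concerns one item of 14, before randomization and in the double-blind period. The extension is left out because use there is decided case by case.

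This rests on two assumptions: that the summary of changes reports Appendix 16 accurately, and that the sponsor meant the listing of juice to have effect.

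Two further inferences are tempting and unsupported:

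- **Raised ASN51 exposure or a longer PR interval.** The text available documents no effect of juice on either. The AESI explains why clear instructions matter; it is not evidence of harm.
- **Bias in the efficacy analyses.** The key secondary and tau PET estimands (9.3, 9.4.1) apply a treatment policy strategy to concomitant medication use in the mITT set. No effect on those analyses, or on power or sample size, is shown.

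**What to change.** Reword 5.5.1 along these lines: *No restrictions, except that dietary items listed in Appendix 16 as moderate or strong CYP3A4 or CYP2C19 inhibitors (e.g., grapefruit juice) must be avoided before randomization and throughout the DB Intervention Period, as specified in exclusions 41 and 42 and Section 6.8.1.*

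The sponsor should also state in Appendix 16 how many days before Day 1 juice must be avoided. The existing washouts (5 half-lives in exclusions 41 and 42; the lesser of 5 half-lives or 30 days in 6.8.1) do not readily apply to a juice. The documents give no basis for choosing the number here. The same line should go into the participant dosing instructions.

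Deleting grapefruit juice from Appendix 16 would also remove the mismatch, but it would undo part of a revision made on FDA feedback and is not recommended.

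Cost: one sentence in 5.5.1, one interval in Appendix 16 and one line in the dosing instructions, with no new visit, sample or data field. The downside is a minor dietary limit for participants.

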5.5.2 Physical Activity

No restrictions.

5.5.3 Other Activity

Participants must refrain from donating blood or blood products from the screening visit until 1 month after the last dose of ASN51.

Male participants should refrain from sperm donation from the screening visit until 90 days after the last dose of ASN51.

5.6 Screen Failures

Prospective participants will be evaluated for eligibility per inclusion and exclusion criteria (Sections 5.3 and 5.4) as detailed in Section 8.1 and Table 1.

An individual who does not meet any inclusion criteria or meets one or more exclusion criteria will be deemed ineligible; the reason for screen failure will be documented. No exceptions to eligibility criteria (i.e., protocol waivers) will be granted.

Rescreening may be considered in consultation with the Medical Monitor if there is a change in the individual's status. Rescreening is not allowed if the reason for screen failure is an imaging test for AD or biomarker unless due to technical issue with sample or processing. An abnormal laboratory test result may be repeated once within the screening period without the participant being considered a rescreen.

6 INTERVENTIONS AND CONCOMITANT THERAPY

Site staff should follow the Pharmacy Manual for specific instructions on the handling, preparation, administration, and disposal of the study treatment.

Study treatment must be dispensed only by a pharmacist or appropriately qualified staff. Study treatment is to be dispensed only to participants enrolled in this study. Once study treatment is prepared for a participant, it can be administered only to that participant. Study treatment are for one-time use only; do not use any study treatment remaining in the vial for another participant.

6.1 Description of Trial Intervention

Eligible participants will be randomized in a 1:1:1 ratio to receive ASN51 ASN51 or placebo. To maintain the blind, all participants will take a total of 4 capsules by mouth once a day as summarized in Table 4.

Table 4 Trial Interventions: Daily Dose Administration

Randomized Assignment	Number of ASN51 Capsules	Number of Matched Placebo Capsules	Total Capsules Administered (orally, once daily)
ASN	2	2	4
ASN	4	0	4
Placebo	0	4	4

6.1.1 Investigational Medicinal Product: ASN51

The investigational medicinal product (IMP), ASN51, is a reversible and substrate competitive small molecule inhibitor of O-GlcNAcase. ASN51 drug product formulation is supplied in capsule form at the free base equivalent dosage strength. ASN51 is intended for oral administration.

The IMP is manufactured, packaged, and labeled according to current Good Manufacturing Practice regulations.

6.1.2 Control/Comparator: Placebo

Placebo capsules (equivalent to ASN51) will be matched in color, shape, size, and number of capsules. Placebo capsules will serve as a control for the DB Intervention Period, and to maintain the blind for participants assigned to receive ASN51

No active comparator or any other additional drug products will be provided as part of the trial.

6.2 Rationale for Trial Intervention

6.3 Dosing and Administration

All participants will take a total of ASN51 and/or placebo capsules once daily to achieve the assigned dose level and maintain the blind.

Participants will be provided with dosing instructions; capsules will be taken orally, with or without food, and should be administered approximately the same time each day, preferably in the morning.

For any dose not taken within 12 hours (\pm 2 hours) of the usual time, or within 12 hours (\pm 2 hours) of prior dose participants will be instructed to withhold dosing on that day. Participants will be instructed not to make up the missed doses.

If drug-related tolerability issues are suspected for an individual participant, contact the Sponsor Medical Monitor for guidance.

6.4 Treatment of Overdose

No antidotes or antagonists exist for the treatment of a potential ASN51 overdose. Clinical symptoms will be treated as deemed appropriate by the Investigator and/or treating physician.

All AEs associated with overdose should be documented in the electronic case report form (eCRF) and reported following procedures for the reporting of Serious Adverse Events (Section 12.3).

6.5 Preparation, Handling, Storage, and Accountability

6.5.1 Preparation of Trial Intervention

ASN51 will be supplied in capsule form and dispensed to the participant.

During the DB Intervention Period, matched placebo will be supplied in capsule form and dispensed to the participant as assigned.

